### Randomization:

An envelope with 42 identical slips of paper with 21 labeled LipiFlow and 21 labeled iLux will be prepared prior to initiating the study for a 1:1 randomization ratio. After a subject has been

determined to meet entrance criteria and has signed the ICF, each subject will draw one slip of paper which will determine whether they receive either Lipiflow first or iLux first.

#### Criteria for subject withdrawal by investigator

Subjects may be withdrawn from study treatment at any time if, in the opinion of the Investigator, continued treatment poses a risk to the subject.

#### Statistical Analysis Plan

Descriptive statistics will be provided to summarize each treatment questionnaire response: N, mean, standard deviation, minimum, maximum, and median. Categorical or binary endpoints will be summarized by count and percentage. Other statistical tests of correlation, variance, or regression to be recommended by statistician and methods used will be reported in the final report.

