### Total Number of Participants to be Enrolled:

The clinical site will enroll up to 42 subjects to ensure that 38 subjects have evaluable data for both treatments. With 38 evaluable subjects, this study will have 80% power to detect a half point difference between treatments on the 5-point Likert-style questionnaire, assuming within patient standard deviation of 0.75 points and at a significance level of 0.05.

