## **Study Design / Methods / Procedures**

This study is an open-label, single site, crossover trial comparing LipiFlow Thermal Pulsation System to the iLux System based on patient acceptance, comfort, and preference. The proposed sample size is 42 subjects allowing for 10% dropout during patient screening.

2 Visits: Screening visit and Study visit

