### Screening visit (approx. 30 min)

1. Obtain Informed Consent
2. Obtain Patient demographics
3. Verify Inclusion and Exclusion criteria
4. Schedule for Study visit
5. Randomize in a 1:1 ratio to receive bilateral treatment initially with either LipiFlow or iLux

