### Informed Consent (*Sterling IRB- Informed Consent Document Preparation service requested*)

Patients must have the study explained to them by a member of the study team, they must be provided enough time to consider their participation in the study and provided an opportunity to ask questions of the study team. Subjects must sign the most current version of an informed consent form (ICF) written and approved by an Institutional Review Board (IRB). All patients who sign an ICF are considered enrolled subjects in the study and will not undergo any study-specific assessments until after they have signed the ICF. Subjects may withdraw their consent to participate in the study at any time, for any reason. The study investigator may also withdraw subjects from the study at their discretion in order to protect the rights, safety, or welfare of the subject. All withdrawn subjects will be included in study analyses, but they will not be replaced. No missing data will be imputed.

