## Lipiflow vs. iLux Patient Acceptance and Comfort Study Questionnaire

Subject Number:

Gender:

Date:

Time:

Bilateral Procedure 1: (Circle One)

Lipiflow

iLux

Q1 - This was a comfortable procedure.

1                      2                      3                      4                      5  
Strongly Disagree    Disagree            Undecided            Agree                Strongly Agree

Q2 - I would have this procedure again.

1                      2                      3                      4                      5  
Strongly Disagree    Disagree            Undecided            Agree                Strongly Agree

Q3 - I would recommend this procedure to my friends or family.

1                      2                      3                      4                      5  
Strongly Disagree    Disagree            Undecided            Agree                Strongly Agree

Q4 - My perception of the study doctor changed because of this procedure.

1                      2                      3                      4                      5  
More Negative        Slightly More Negative    Unchanged            Slightly More Positive    More Positive

Q5 - This was a Positive overall experience.

1                      2                      3                      4                      5  
Strongly Disagree    Disagree            Undecided            Agree                Strongly Agree

Subject Number:

Gender:

Date:

Time:

Bilateral Procedure 2: (Circle One)

Lipiflow

iLux

Q1 - This was a comfortable procedure.

1 2 3 4 5  
Strongly Disagree Disagree Undecided Agree Strongly Agree

Q2 - I would have this procedure again.

1 2 3 4 5  
Strongly Disagree Disagree Undecided Agree Strongly Agree

Q3 - I would recommend this procedure to my friends or family.

1 2 3 4 5  
Strongly Disagree Disagree Undecided Agree Strongly Agree

Q4 - My perception of the study doctor changed because of this procedure.

1 2 3 4 5  
More Negative Slightly More Negative Unchanged Slightly More Positive More Positive

Q5 - This was a Positive overall experience.

1 2 3 4 5  
Strongly Disagree Disagree Undecided Agree Strongly Agree

Final Question - Which procedure did you prefer?

(circle one)

Lipiflow

iLux

No Preference

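### Treatment order is randomised and recorded in this same-day crossover, but the analysis plan commits to nothing that uses it

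*Combined protocol and SAP*

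**What the plan says.** The Study Design section describes a "crossover trial comparing LipiFlow Thermal Pulsation System to the iLux System based on patient acceptance, comfort, and preference". At screening, subjects are allocated by order: "Randomize in a 1:1 ratio to receive bilateral treatment initially with either LipiFlow or iLux". The Randomization section adds that "each subject will draw one slip of paper which will determine whether they receive either Lipiflow first or iLux first", using 21 slips for each order. The questionnaire has one form for Procedure 1 and another for Procedure 2, each with the device circled and the date and time entered, so order is captured for every rating.

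The sample size section bases 80% power on 38 evaluable subjects and a half-point difference, "assuming within patient standard deviation of 0.75 points and at a significance level of 0.05". That is a within-subject comparison.

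The Statistical Analysis Plan section promises: "Descriptive statistics will be provided to summarize each treatment questionnaire response: N, mean, standard deviation, minimum, maximum, and median". It adds counts and percentages for categorical or binary endpoints, which would cover the final preference question. It then says: "Other statistical tests of correlation, variance, or regression to be recommended by statistician and methods used will be reported in the final report". No section mentions period, sequence or order in the analysis, and none plans a table by order.

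On losses, the Informed Consent section says "All withdrawn subjects will be included in study analyses, but they will not be replaced", and that missing data are not imputed.

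**The concern.** Each subject rates a second procedure on the same eyes, on the same day, after having experienced the first. Ratings could move between the two occasions whichever device is used. Randomising the order keeps such a shift from favouring one device, but the analysis has to use the order to remove the shift from the error term. If it does not, the shift pushes the within-subject differences of the two order groups apart, and an unadjusted paired test counts that spread as noise.

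The summaries that the plan does commit to use neither the pairing nor the order. A reader of the per-treatment tables could not tell whether second-procedure ratings differ from first-procedure ratings. The deferral clause allows a period term but does not require one, so the choice would be made after open-label data exist. At stake are precision and transparency, not false positives.

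**Working it through.** **Inputs.** From the sample size section: N = 38 evaluable of 42 enrolled, difference τ = 0.5, within-patient SD 0.75, significance level 0.05. From the Randomization section: 21 subjects per order. Assumed: a two-sided test (sidedness is not stated, but two-sided reproduces 38), normally distributed differences, and a shift π between second and first procedure of 0.25, 0.5, 0.75 or 1.0 point. The plan names no test, so the paired t-test is a comparator chosen for this check.

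**The plan's own figure.** The SD of the within-subject difference is 0.75 × √2 = 1.061 (variance 1.125). By the noncentral t distribution, a paired t-test (37 df) at N = 38 has 80.8% power, and 37 subjects would give 79.7%. The stated 80% is reproduced. The period-adjusted crossover test (36 df) has 80.7% at 19/19, 80.6% at 20/18 and 80.3% at 21/17.

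**Effect of ignoring order.** Let d be the LipiFlow rating minus the iLux rating, with n1 subjects LipiFlow-first and n2 iLux-first.

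- The mean of d is τ − π in the LipiFlow-first group and τ + π in the iLux-first group.
- The bias of the overall mean is −π(n1 − n2)/N, which is zero at 19/19.
- The expected sample variance of d is σ² + 4π²·n1·n2/[N(N − 1)], where σ² is the variance of d with period removed. At 19/19 this is σ² + π² × 38/37.

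Power without period was obtained by numerical integration, with a normal mean and a noncentral chi-square sum of squares. Power with period is by noncentral t.

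The documents leave open what 0.75 covers. **Reading A:** it excludes period variation, so σ² = 1.125. **Reading B:** it already includes it, so σ² = 1.125 − π². Results at 19/19:

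| Shift π | A: power without period | A: power with period | A: 95% CI half-width without period | A: N for 80% power without period | A: type I error without period | B: power without period | B: power with period |
|---|---|---|---|---|---|---|---|
| 0.25 | 79.2% | 80.7% | 0.358 | 40 | 4.4% | 81.4% | 82.9% |
| 0.5 | 74.3% | 80.7% | 0.386 | 44 | 3.1% | 83.5% | 89.4% |
| 0.75 | 66.0% | 80.7% | 0.429 | 50 | 1.7% | 88.3% | 97.9% |
| 1.0 | 54.5% | 80.7% | 0.482 | 60 | 0.7% | 99.3% | near 100% |

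With period in the model, the half-width under reading A is 2.028 × 1.061/√38 = 0.349 at every shift. Without it, at π = 0.5, the SD is √(1.125 + 0.25 × 38/37) = 1.175, which gives 0.386.

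**Unequal orders.** If 4 of 42 are lost at random, the hypergeometric probabilities are 39% for 19/19, 50% for 20/18 either way and 11% for 21/17 either way. At 21/17 the bias is (4/38)π, which is 0.026, 0.053, 0.079 and 0.105 point for the four shifts. In the unfavourable direction (probability 5.3%), power without period at π = 0.5 under reading A is 64.1%. Averaged over all splits, power without period is 79%, 74%, 66% and 54%, so imbalance adds almost nothing on average. Type I error averages 4.5%, 3.2%, 1.9% and 1.0% and stays below 5% at every split.

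**The case against.** The strongest objection is that the plan names no device comparison at all, so a missing period term is one detail of a larger gap, and the unadjusted paired test is not the plan's own analysis. That is fair, and the fix therefore has to state the comparison itself. The point about order remains, because naming a plain paired test would close the larger gap and still lose the precision.

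The shifts are not documented. Those of 0.75 and 1.0 point are 1 to 1.33 times the stated SD and 1.5 to 2 times the target difference, so the range up to 0.5 deserves most weight. At a shift of 0.1 under reading A, power is 80.5% without period and 80.7% with it. Under reading B the unadjusted test never falls below the stated 80%; adjustment is then an improvement, not the repair of a shortfall. The calculations also assume normality, whereas the outcomes are single 5-point items that can reach a floor or ceiling, and the sample size section does not say which item it concerns. All of this limits the size of the effect but not its direction.

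Losses between the two procedures may be few: both take place in one visit, and the 10% allowance is described as dropout at screening. The gain from keeping first-period ratings may then be small. Finally, since order is recorded, the statistician could still use it later. That is true, but nothing commits to it, and no table by order is promised.

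**Conclusion.** The point holds, as a minor one. The plan randomises and records order and powers a within-subject comparison, but commits to no analysis or table that uses order. Under reading A, leaving period out costs 1.5 points of power at a 0.25 shift (80.7 − 79.2) and 6.4 points at a 0.5 shift (80.7 − 74.3); only larger shifts cost more. Under reading B the stated power is kept, but adjustment would still add 1.5 points (82.9 − 81.4) and 5.9 points (89.4 − 83.5). There is no inflation of type I error and, with balanced orders, no bias. These sizes rest on assumed shifts, normal differences and a two-sided test. That nothing commits to using order rests on the text alone.

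**What to change.** Add to the Statistical Analysis Plan section:

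1. Compare the devices on each item with a crossover analysis that includes period, and report the difference with a 95% CI. Either a mixed model (device and period fixed, subject random) or a comparison of within-subject differences between the two orders would serve; a rank-based version is acceptable for 5-point items. The mixed model also keeps first-procedure ratings from anyone withdrawn before the second device, in line with the rule that withdrawn subjects are analysed.
2. Report N, mean and SD of each item by order and period, and the preference question by order, including the no-preference answer.
3. State that the period term does not correct for carryover, which this design cannot resolve.

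A first-procedure-only estimate and an order-adjusted preference test are optional and supportive only. The interval between treatments is not questioned here.

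The cost is SAP wording, a few tables from data already collected, and one degree of freedom. With no period effect, power goes from 80.8% to 80.7% at 19/19, or to 80.3% at 21/17. No new subjects, visits or data are needed.

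### The SAP commits to no within-subject analysis of the half-point device difference the trial is sized for, and the available text names no item or score to carry it

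*Combined protocol and SAP*

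**What the plan says.** The section on the number of participants makes a confirmatory statement. It wants enough enrolment that "38 subjects have evaluable data for both treatments", and with that number "this study will have 80% power to detect a half point difference between treatments on the 5-point Likert-style questionnaire". The variability and error rate behind this claim are stated in the same sentence: "assuming within patient standard deviation of 0.75 points and at a significance level of 0.05".

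Study Design describes an "open-label, single site, crossover trial comparing LipiFlow Thermal Pulsation System to the iLux System based on patient acceptance, comfort, and preference". None of the three concepts is ranked first. The order of treatment is randomized by drawing from "42 identical slips of paper with 21 labeled LipiFlow and 21 labeled iLux".

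The Statistical Analysis Plan is one short paragraph. Its commitments are "Descriptive statistics will be provided to summarize each treatment questionnaire response: N, mean, standard deviation, minimum, maximum, and median" and "Categorical or binary endpoints will be summarized by count and percentage". On inference it says only "Other statistical tests of correlation, variance, or regression to be recommended by statistician and methods used will be reported in the final report".

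The questionnaire at the end of the document has five items scored 1 to 5, completed once after each procedure, and one final preference question. It gives no total, mean or other scoring rule.

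**The concern.** The sample size statement and the SAP do not meet. The first attaches a significance level and a power to a difference between devices within patients. The second plans a summary of each device separately and names no analysis of that difference.

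Two things are at stake. First, a reader who follows the SAP can subtract two means but cannot attach a standard error, because that depends on the within-subject correlation, which per-device SDs do not show. Second, with five items, no named outcome in the available text, no named test and no date for choosing either, both choices could be made after the responses are known. The trial is open-label, so nothing in the design prevents this. The 0.05 and the 80% then lose their stated meaning.

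**Working it through.** **Inputs from the sample size section:** difference 0.5, within-patient SD 0.75, level 0.05, 38 evaluable subjects. Sidedness is not stated.

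**1. Reproduce the plan's figure.**
- SD of a within-patient difference = 0.75 × √2 = 1.061.
- Standard error at n = 38: 1.061/√38 = 0.172. Noncentrality = 0.5/0.172 = 2.91.
- Noncentral t, two-sided 0.05, 37 df: power 80.8%. At n = 37 it is 79.7%. So 38 is the smallest n that reaches 80%.
- With a period term (36 df at n = 38): 80.7% at 38 and 79.6% at 37.
- Readings that do not fit: a one-sided test needs 30 subjects. If 0.75 were already the SD of the difference, 20 subjects would do, and 38 would give 97.9%.

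The figure therefore rests on a two-sided within-patient comparison of one score.

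**2. What the SAP's summaries can and cannot give.** With the same SD s for each device and within-subject correlation r, the SD of the difference is s√(2(1 − r)). Take s = 1.061 for illustration, with assumed r:

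| r | SD of difference | SE at n = 38 |
|---|---|---|
| 0 | 1.500 | 0.243 |
| 0.5 | 1.061 | 0.172 |
| 0.7 | 0.822 | 0.133 |

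The per-device table would look the same in all three rows.

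**3. Leaving the item open.** Suppose all five items were tested at 0.05 without correction.
- Independent items: 1 − 0.95⁵ = 22.6%.
- Simulation of 100,000 trials with n = 38 and period-adjusted tests, at assumed correlations between item differences of 0.5, 0.8 and 0.9: 18.5%, 12.9% and 10.4%.
- Bonferroni at 0.05/5 = 0.01 would leave 57.8% power per item at n = 38, and 56 evaluable subjects would be needed to restore 80%.

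**4. Leaving the score open.** If 0.75 is a per-item SD and the outcome were the five-item mean, the SD of the difference is 1.061 × √((1 + 4r)/5), where r is now the correlation between item differences. At assumed r = 0.9 this is 1.017 (power 83.8%). At r = 0.5 it is 0.822 (power 95.4%). The stated 80% thus depends on which outcome is meant.

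**5. Cost of a period-adjusted analysis.** SE = (1.061/2) × √(1/n₁ + 1/n₂), where n₁ and n₂ are the numbers in each order.
- 19 and 19: SE 0.172, 95% CI half-width 0.349, power 80.7%.
- 17 and 21 (all four losses from one order): SE 0.173, half-width 0.351, power 80.3%.
- In simulation with 19 per order, an assumed period effect of 0.25 or 0.5 point lowers the plain paired t-test to 79.3% or 74.4%. The adjusted analysis stays at 80.7% to 80.8%.

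**The case against.** The strongest reply is that the intended analysis can be recovered. The sizing uses a within-patient SD, requires data on both devices, and reproduces only as a two-sided within-patient test. Both questionnaires carry the subject number, so pairs can be formed. The SAP's mention of variance and regression covers families that include a crossover model. This stands as evidence of what the sizing assumed. It does not make that analysis a commitment: the SAP never adopts it, and its wording is too general to identify a method.

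Several stronger readings are tempting, and the documents do not support them:
- **That the method stays open until the final report.** The SAP says the methods will be reported there, not chosen there. The accurate statement is that no time is set.
- **That the protocol names no primary outcome anywhere.** An opening section was not available for review and may name one.
- **That the items cannot be combined because Q4 has different anchors.** Q4 is also scored 1 to 5 with higher more favourable, in the same direction as the others. The gap is only that no scoring rule is given.
- **That the trial intends five uncorrected tests.** No section proposes this, nor a Bonferroni correction or a five-item mean. The figures for these show what is at risk, not an error already made.

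**Conclusion.** The point holds. Followed as written, the SAP commits to no estimate, interval or test for the contrast on which the trial is powered. Confidence is high that no test is named and that no time is set for choosing one. It is moderate that no outcome is named, because of the unavailable section.

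A reader might infer that 38 is the wrong number. It is not: the arithmetic reproduces, and nothing here questions the crossover design. The defect is that the 80% and the 0.05 belong to an analysis the SAP does not contain.

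The possible familywise error of about 10% to 23% is conditional on uncorrected testing of all five items and on assumed correlations of 0.9 to 0. The documents give none of these correlations. The absence of a committed analysis does not depend on them.

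**What to change.** Before outcome data are examined, replace the last sentence of the Statistical Analysis Plan with text such as:

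> The primary outcome is [one item or one defined 1–5 score, named by the sponsor, unless already named elsewhere in the protocol]. The primary analysis is the within-subject LipiFlow minus iLux difference, adjusted for period, two-sided alpha 0.05, with a 95% CI; it assumes no unequal carryover between the same-day treatments. The mean and SD of the paired difference are reported beside the per-device summaries. The remaining items and the preference question are reported with 95% CIs and carry no separate 0.05 claim.

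The period term suits a design in which order is randomized and both procedures fall on one day. A rank-based sensitivity analysis is optional. If outcome data have already been seen, the choice should be labelled post hoc.

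Cost: one paragraph, with no added visits or data. The number evaluable stays at 38 provided the chosen outcome keeps the 0.5-point and 0.75 assumptions. A summed score would not, and the sizing would have to be redone. The period term costs about 0.1 percentage point of power (80.8% to 80.7%). The real concession is that only one outcome carries the 0.05 claim.

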#### Storage of Data

All study data will be stored at Phoenix Eye Care in a locked secure location with restricted access.

#### Data Confidentiality

Subjects will be assigned Subject numbers, which will only be identifiable by the investigator and study coordinator.

### **Risk / Benefit assessment**

#### Risks

- 1- Eyelid irritation, redness, or inflammation
- 2- Ocular irritation, redness, or inflammation
- 3- Ocular symptoms – tearing, itching, redness, temporary visual blur

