### Exclusion Criteria:

1. History of intraocular or oculoplastic surgery within 6 months of Screening visit
2. History of ocular injury or trauma, chemical burns, or limbal stem cell deficiency within 3 months of the Screening visit
3. Active ocular infection or active ocular inflammation (including allergic conjunctivitis, vernal or giant papillary conjunctivitis) at time of Screening visit
4. History of ocular surface abnormality that may compromise corneal integrity
5. History of treatment with LipiFlow or iLux in either eye in the last 6 months
6. Allergy to topical proparacaine eye drops

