### Study visit (approx. 100 min)

1. Perform slit lamp evaluation to verify no abnormal clinical findings prior to treatment
2. Perform either bilateral Lipiflow or bilateral iLux per Screening visit randomization
3. Patient fills out 5 Point Likert Scale questionnaire about treatment received
4. Perform slit lamp evaluation to verify no abnormal clinical findings prior to treatment
5. Perform the other bilateral Lipiflow or bilateral iLux procedure  $\geq$  1-hour after first
6. Patient fills out 5 Point Likert Scale questionnaire about treatment received
7. Patient answers final Patient Preference Question

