### Treatments

Both procedures will be performed on both eyes on the same day at least one (1) hour apart.

1. Eye makeup shall be removed.
2. The device shall be prepared for use in accordance with the Instructions per User Manual for the device to which the subject is randomized.
3. Proparacaine eye drops will be instilled in both eyes.
4. Therapy will be delivered in accordance with the User Manual for the device to which the subject is randomized.
5. Throughout the treatment visit, subjects will be assessed for any adverse events.

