### Safety monitoring

1. Assess and record any adverse events that are observed or reported by the subject
2. Assess and record any treatment device deficiency

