#### Adverse events

After each treatment and the subject having had an opportunity to spontaneously mention any problems, the Investigator should inquire about adverse events. All adverse events will be recorded on a separate adverse events form.

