#### Benefits

- 1- Unblocking of inspissated meibomian glands
- 2- Improvement in dry eye symptoms – tearing, itching, redness

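### Tearing, itching and redness are listed as both treatment risks and dry eye symptoms, with no symptom record before the first device and no new-or-worse rule, so per-device counts of symptom events can mix background disease and carry-over with device effects

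*Combined protocol and SAP*

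**What the plan says.** - **Risk / Benefit assessment, Risks:** the ocular symptoms listed are "tearing, itching, redness, temporary visual blur".
- **Risk / Benefit assessment, Benefits:** "Improvement in dry eye symptoms – tearing, itching, redness". Three of the four listed risks are thus also symptoms of the condition under treatment. Temporary blur is not.
- **Screening visit:** the only descriptive data step is "Obtain Patient demographics". The other steps are consent, eligibility, scheduling and randomization.
- **Exclusion Criteria:** "Active ocular infection or active ocular inflammation (including allergic conjunctivitis, vernal or giant papillary conjunctivitis) at time of Screening visit". This applies at Screening and does not cover tearing or itching as such.
- **Study visit, steps 1 and 4:** before each device, "Perform slit lamp evaluation to verify no abnormal clinical findings prior to treatment". No grading is named, nor any form for the findings.
- **Treatments:** "Throughout the treatment visit, subjects will be assessed for any adverse events".
- **Safety monitoring:** "Assess and record any adverse events that are observed or reported by the subject".
- **Adverse events:** "After each treatment and the subject having had an opportunity to spontaneously mention any problems, the Investigator should inquire about adverse events". Events go on a separate form, which the document does not reproduce.
- **Questionnaire:** completed after each procedure. Its five items and the final preference question ask about no ocular symptom.

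The document does not define an adverse event as new or worse than a reference state. It gives no rule on relatedness, and none for a complaint that continues from the first procedure into the second. The Statistical Analysis Plan section does not mention adverse events.

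**The concern.** Subjects have confirmed meibomian gland dysfunction and are recruited from patients seen for dry eye evaluations, so some can be expected to arrive with tearing, itching or redness. If one of them mentions itching when asked after the first procedure, nothing on record shows whether it was there an hour earlier. The second procedure follows on the same day, possibly after only one hour. A complaint after it could be background disease, carry-over from the first device or an effect of the second.

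At stake is what the by-device listing of symptom-type adverse events can be taken to mean. The gap cannot be repaired at analysis, because a symptom state that was never recorded cannot be rebuilt after the visit.

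**Working it through.** **1. The plan's own figure.** The only calculated number is the sample size, and it does not concern adverse events. With a within-patient SD of 0.75, the SD of a paired difference is 0.75 × √2 = 1.061. For a 0.5-point difference at two-sided 0.05 (sidedness assumed), a paired t-test with 38 subjects has power 0.808. The stated 38 subjects and 80% power reproduce, and nothing below changes them.

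**2. Reference available before each device.**

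| | Before first device | Before second device |
|---|---|---|
| Redness | Slit lamp, step 1; no recording specified | Slit lamp, step 4; no recording specified |
| Tearing, itching | None | Inquiry after the first device and surveillance during the visit; no rule for use |
| Blur | None | As for tearing and itching |

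The gap is complete for tearing, itching and blur before the first device. It is partial for redness, and partial for all of them before the second device.

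**3. Inflation and dilution (illustration).** The document gives no symptom or event rates, so all rates here are assumed. Let π be the share of subjects with a prior symptom, all counted as events under both devices. Let d be the rate of new symptoms among the rest. The observed rate is π + (1 − π)d, the background share is π / [π + (1 − π)d], and the observed contrast is (1 − π)(d₂ − d₁).

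| π | Count of 38, d = 10% | Background share | Observed contrast when truth is 10% v 30% |
|---|---|---|---|
| 0 | 3.8 | 0% | 0.20 |
| 20% | 10.6 | 71% | 0.16 |
| 40% | 17.5 | 87% | 0.12 |
| 60% | 24.3 | 94% | 0.08 |
| 80% | 31.2 | 98% | 0.04 |

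When the two devices have equal effects, the contrast is 0 at every π. Background disease counted under both devices creates no false difference.

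**4. Chance imbalance if ongoing complaints are logged only once.** Suppose a prior complaint is logged after the first device and not again. With 21 subjects starting on each device (Randomization section), background events per device are Binomial(21, p), and the difference has SD √[2 × 21 × p(1 − p)].

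- p = 20%: mean 4.2 per device, SD 2.59, probability of a gap of 4 or more 0.17.
- p = 40%: mean 8.4, SD 3.17, probability 0.27.
- p = 60%: mean 12.6, SD 3.17, probability 0.27.

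This is the worst case. If half of the complaints are logged after both devices, those cancel and p is replaced by p/2. The probabilities become 0.07, 0.17 and 0.24. If all are logged after both, the probability is 0.

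**The case against.** The strongest reply has four parts.

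*The recording rule covers adverse events, not every complaint.* This is correct. Nothing directs staff to log a long-standing itch as an event. But the term is left undefined, and no recorded arrival state exists against which to judge it. The separate form may capture onset, severity or relatedness. It is not shown, so that can be neither credited nor denied.

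*A reader might infer that the second device has no reference at all.* The document does not support that. The inquiry follows each treatment, surveillance runs through the visit, and a slit lamp check precedes the second device. What is missing is a rule for using them and a symptom record made just before that device.

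*A reader might infer that adverse-event counts cannot separate device effects from dry eye, or that a comparison would reflect order and background disease in place of the devices.* That goes too far. Each subject receives both devices in randomized order, redness is visible at the slit lamp, and active inflammation is excluded at Screening. Prior disease bears on both devices alike, so it mainly dilutes the contrast. Chance imbalance arises only to the extent that complaints are logged once.

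*No between-device safety test is planned.* This stands. The stated purpose is acceptance, comfort and preference, and the power statement concerns the questionnaire. It limits the importance of the point but does not remove it, because the study still commits to collecting adverse events after each device.

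**Conclusion.** The point holds for symptom-type adverse events, chiefly tearing and itching. As written, the plan lets per-device counts of these mix existing dry eye, and carry-over from the first device, with new device effects. The main consequences are inflated counts and a diluted contrast. If 20% to 80% of subjects arrive symptomatic and all are counted, background makes up 71% to 98% of the count at an assumed 10% device rate, and a true 0.20 contrast shrinks to between 0.16 and 0.04.

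Chance imbalance is a secondary risk. A gap of four or more background events in 17% to 27% of trials is a worst case: it assumes 20% to 60% prior symptoms, each logged only after the first device.

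The document supports none of these rates, so the sizes are illustrative and only the mechanism is established. The effect is confined to the safety listing. The acceptance, comfort and preference results and the sample size do not change. This is a cheap improvement worth making before enrolment, not a flaw in the main comparison.

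**What to change.** - At Study visit steps 1 and 4, before each device, ask about and record the presence and severity (none, mild, moderate, severe) of each symptom in the Risks list. Record redness seen at the slit lamp at the same time.
- Ask the same short list at the inquiry after each device, once the subject has had the chance to volunteer problems.
- State that a symptom counts as an adverse event for a device only if it is new or worse than the record made just before that device.
- List events by device, separately for first and second procedures, so that possible carry-over can be seen.

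The cost is a half-page form and a few minutes per visit, at existing steps, with no new examination or staff. The downside is that direct questions may raise the number of mild events recorded, for both devices. A lighter option is one question on arrival plus a one-line definition of new or worse. It would supply the missing reference for the first device but would leave carry-over into the second unresolved.
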